5.1 INCLUSION CRITERIA

Patients must satisfy all the following inclusion criteria to be enrolled in the study:

1. Diagnosis of probable or definite ALS according to the revised El Escorial criteria [29], with bulbar onset of disease, familial or sporadic form,
2. Onset of symptoms \leq 18 months prior to screening, as reported by the patient,
3. Adult males or females, aged at least 18 years old,
4. SVC $>$ 60% of predicted value for age and sex,
5. ALSFRS-R score \geq 36,
6. Treatment with riluzole 100 mg/day, at stable dose since at least one month and well tolerated,
7. Male or female patient of childbearing potential¹⁰ who agrees to use highly effective mechanical contraception methods (sexual abstinence, intrauterine device, bilateral tubal occlusion, vasectomised partner) throughout the study, and for 3 months after the end of the treatment,
8. Patient who read, understood and signed the ICF,
9. Patient who is willing to adhere to the study visit schedule and is capable to understand and comply with protocol requirements.

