5.3 WITHDRAWAL OF THE PATIENT

Patients may withdraw from the study at any time without having to provide justification and without penalty to their continuing medical care.

The investigators may withdraw patients from the study for the following reasons:

- Patient withdrawing the consent,
- If, in the investigator's opinion, continuation in the study would be detrimental to the patient's well-being, in particular in case of an AE,
- If, in the investigator's opinion, the patient is unable to maintain the schedule or is non-compliant,

¹¹ Decline will be calculated as follows: 48 minus ALSFRS-R score at the time of inclusion divided by number of months since occurrence of first symptoms of disease, as reported by the patient.

- If the patient becomes pregnant during the study,
- If the patient meets one of the following criteria for permanent drug discontinuation:
 - Increased ALT or AST levels $\geq 5 \times$ ULN.
 - ALT or AST > 3 ULN and total bilirubin levels > 2 ULN.
 - Neutropenia.
 - Symptoms evocative of interstitial lung disease: dry cough and/or dyspnoea, bilateral diffuse lung opacities.
- Lost to FU. A participant will be considered lost to FU if he/she repeatedly fails to return for scheduled visits and is unable to be contacted by the study site. Site personnel are expected to make diligent attempts to contact participants who fail to return for a scheduled visit or are otherwise unable to be followed up by the site.

The date of withdrawal and the principal reason for withdrawal must be recorded in the eCRF and in the patient's records. No additional data will be collected for withdrawn patients. Every effort must be made to contact patients who did not come back for a planned visit/contact.

Every effort will be made to ensure that patients who do not complete all study visits return to the site for the premature discontinuation visit ([Section 4.1.9](#)), as soon as possible and no later than 4 weeks after the last IMP intake. Patients who withdraw due to an AE or SAE will be given appropriate care under medical supervision until the symptoms resolve or the patient's condition becomes stable.

Patients who prematurely withdrew from the study or are lost to FU will not be replaced by new patients.

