8.1.5.2 Secondary outcomes

Efficacy endpoints

Analyses will be further detailed in the SAP.

The analysis of efficacy endpoints will be primarily performed in the FAS. A secondary analysis will be proposed in the PPS.

- Change in ALSFRS-R score: from baseline to 6 months will be analysed using a mixed model for repeated measures (MMRM) assuming missing at random (MAR) and unstructured covariance matrix and including fixed factors for treatment, visit (categorical variable), treatment-by-visit interaction, random patient factor and baseline ALSFRS-R as a continuous covariate. The degrees of freedom will be estimated using the Kenward-Roger's approximation. Least square means (LSMs) of change from baseline and LSM differences in change from baseline between active doses and placebo will be presented along with 80% and 95% CIs and the comparison p-value. A one-sided nominal significance level of 0.10 will be used for treatment comparison. Model assumptions will be checked (plot of studentized residuals vs predicted values, etc.). If the model assumptions do not hold, a rank

semi-parametric analysis of covariance (ANCOVA) model (or a rank non-parametric Quade's ANCOVA model if the assumptions of this latter do still not hold) will be proposed instead. As the MAR assumption is untestable and may not hold for subjects withdrawing at their own will, a sensitivity analysis will be based on a pattern mixture model that uses a multiple imputation technique analysed with an ANCOVA with pre specified fixed factors and covariates. The imputation model will be further clarified in the SAP. Another sensitivity Bayesian analysis using the historical placebo data from the ProMISe study [26] will be also performed and further detailed in the SAP. An intrapatient analysis of ALSFRS changes will be performed.

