4 RANDOMIZATION

All participants were centrally randomised in a 2:1 allocation ratio to receive either IFB-088 + riluzole or placebo + riluzole, respectively. No stratification factor was considered. The randomisation was performed through an interactive web response system (IWRS) integrated into the eCRF. Before the study is initiated, the log in information and directions for the IWRS was provided to each site. Once a set of medical characteristics is entered, the IWRS immediately assigned a patient to one of the 2 arms. After the randomisation visit, the investigator automatically received a confirmation by email with the treatment number allocated to the patient.

This is a double-blinded study. Neither participants, nor investigators, nor trial staff, nor the sponsor study team was aware of treatment assignments prior to the database lock at the conclusion of the study.

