5.2.23 Subgroup

Five subgroups will be studied:

STATISTICAL ANALYSIS PLAN		
InFlectis BioScience	Sponsor:	InFlectis BioScience
	Protocol Number:	P288ALS
VERSION 1.0 NOV 12, 2024		

- Baseline NFL (neurofilament light chain): \leq median vs $>$ median defined according to the median of baseline NFL of the FAS.
- Country: France vs Italy
- Sex: Man vs Woman
- ALSFRS-R progression rate (point/month) (from symptoms onset to screening visit): \leq median vs $>$ median according to the median of ALSFRS-R progression rate of the FAS.
- Time from onset date of first ALS symptoms to screening: \leq median vs $>$ median according to the median of time from onset date of first ALS symptoms to screening of the FAS.

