5.7 Amyotrophic lateral sclerosis history

The following history of amyotrophic lateral sclerosis will be presented on the Randomization Set by treatment group and overall:

- Time from onset date of first ALS symptoms to screening (months),
- Progression rate at screening
- Time from ALS diagnosis to screening (months),
- Weight at first ALS symptoms onset (kg),
- Weight variation between first ALS symptoms onset and screening (kg) (calculated in the eCRF),
- Type of ALS (Familial, Sporadic, Unknown).

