5.11.2.2 Change in ALSFRS-R total score from baseline to Month 6 (V4)

5.11.2.2.1 Primary analysis

The primary analysis of the Change in ALSFRS-R total score from baseline to Month 6 will be conducted on the FAS patients with a non-missing baseline ALSFRS-R total score as described in Table 1.

Missing data will be handled as described in Table 1 for estimand #1.

STATISTICAL ANALYSIS PLAN		
InFlectis BioScience	Sponsor:	InFlectis BioScience
	Protocol Number:	P288ALS
VERSION 1.0 NOV 12, 2024		

The change in ALSFRS-R score from baseline to Month 6 will be analyzed using an analysis of covariance (ANCOVA) model including treatment (IFB-088 vs placebo), and baseline ALSFRS-R score as continuous covariates. LS mean change with SE and 95% CI by treatment group and the difference in the LS means between 088 and placebo along with SE and 95%CI and p-value will be provided for estimand #1.

Residuals normality will be checked. Homogeneity of slopes across treatment groups will be investigated in an ANCOVA model including an additional term for treatment by baseline ALSFRS-R interaction.

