5.11.2.2.6 Subgroup Analysis

Subgroup analyses will be performed considering Estimand #1 only, based on an ANCOVA model including terms for treatment, subgroup, treatment by subgroup interaction and baseline ALSFRS-R score. Treatment effect with 95% CI and p-value will be estimated by subgroup within this model. P-value of the test for interaction will also be provided.

Subgroups are as follows.

- Baseline NFL (neurofilament light chain): \leq median vs $>$ median
- Country: France vs Italy
- Sex: Man vs Woman
- ALSFRS-R progression rate (point/month) (from symptoms onset to screening visit): \leq median vs $>$ median
- Time from onset date of first ALS symptoms to screening: \leq median vs $>$ median

A forest plot will display the treatment effects by subgroup with 95% CI and p-values and treatment by subgroup interaction p-value

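### Low-cost improvement: no planned analysis gives one overall Month 6 ALSFRS-R treatment effect adjusted for pre-study progression rate, although every patient has that rate at screening

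*SAP*

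**What the plan says.** SAP 5.11.2.2.1 fits an "analysis of covariance (ANCOVA) model including treatment (IFB-088 vs placebo), and baseline ALSFRS-R score as continuous covariates" to the change at Month 6, on the FAS under estimand #1. The same model serves estimands #2 and #3, the per-protocol set and Month 3. The non-parametric analysis is a Wilcoxon/Hodges-Lehmann comparison with no covariate.

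Progression rate appears elsewhere in the plan:

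- Protocol 4.1.1 has it calculated at screening for every patient.
- Protocol 5.2, exclusion criterion 7, bounds it: patients at or below 0.1 or at or above 1.2 points per month are excluded. The footnote defines it as "48 minus ALSFRS-R score at the time of inclusion divided by number of months since occurrence of first symptoms of disease".
- SAP 5.7 tabulates "Progression rate at screening" by arm, together with time from first symptoms.
- SAP 5.2.23 makes "ALSFRS-R progression rate (point/month) (from symptoms onset to screening visit") a median-split subgroup factor. SAP 5.11.2.2.6 analyses it "based on an ANCOVA model including terms for treatment, subgroup, treatment by subgroup interaction and baseline ALSFRS-R score". The reported results are effects within each half and an interaction p-value.

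On allocation, SAP section 4 says: "No stratification factor was considered". Fifty patients were planned at 2:1.

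**The concern.** With about 33 and 17 patients and no stratification, the arms can easily differ by chance in how fast patients were declining before entry. If that rate predicts on-study decline, the planned estimate keeps whatever part of the imbalance baseline ALSFRS-R does not absorb. The table in SAP 5.7 would show the imbalance, and no pre-specified overall estimate would answer it. Any adjustment chosen after unblinding would be open to the charge of selection. What is at stake is how an efficacy signal on a secondary endpoint is read, in a trial that SAP 5.11.1.1 says is not powered for efficacy.

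**Working it through.** **The plan's own figures.** 1 - 0.95^28 = 76.2% and 1 - 0.90^28 = 94.8%; 42/0.85 = 49.4, so 50. All reproduce. No power, SD or effect size is given for ALSFRS-R.

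**Inputs from the documents.** Arms 33 and 17 (50 at 2:1); rate between 0.1 and 1.2 per month; ALSFRS-R at least 36; onset at most "18 months prior to screening, as reported by the patient" (Protocol 5.1).

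**Assumed inputs.** Rate uniform over its eligible range; onset uniform from a floor of 3, 6 or 9 months to 18; outcome SD 5; correlation r of rate with on-study decline from 0 to 0.5; baseline score related to decline only through rate.

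**Step 1: overlap with baseline.** Rate is (48 - score)/months, so given the score it carries only time since onset. Simulated under these limits, its correlation ρ with baseline ALSFRS-R is -0.66 / -0.80 / -0.90 at floors of 3 / 6 / 9 months.

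**Step 2: variance of the treatment difference.** The ratio, rate added to baseline only, is [(1 - r²)/(1 - r²ρ²)] × 46/45. The last factor, 1.022, is the price of one more covariate.

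| r | floor 3 | floor 6 | floor 9 |
|---|---|---|---|
| 0 | 1.022 | 1.022 | 1.022 |
| 0.2 | (0.96/0.983) × 1.022 = 0.999 | (0.96/0.974) × 1.022 = 1.007 | (0.96/0.968) × 1.022 = 1.014 |
| 0.5 | (0.75/0.891) × 1.022 = 0.860 | (0.75/0.840) × 1.022 = 0.913 | (0.75/0.798) × 1.022 = 0.961 |

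Simulated ratios agree: 0.999, 1.007 and 1.015 at r = 0.2; 0.857, 0.916 and 0.963 at r = 0.5. At r of 0 to 0.1, variance rises by about 2% at every floor.

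Break-even is a partial correlation of √(1/46) = 0.147 given baseline. In terms of r this is √[(1/46)/(1 - ρ² × 45/46)], or 0.19 / 0.24 / 0.32.

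**Step 3: power.** For an assumed 2-point effect at the SAP's two-sided 0.20, simulated power at r = 0.5 goes from 0.544 to 0.587 / 0.562 to 0.589 / 0.580 to 0.592. At r = 0.2 it goes from 0.523 to 0.523 / 0.525 to 0.524 / 0.528 to 0.525. At r of 0 to 0.1 it falls by about half a percentage point.

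**Step 4: chance imbalance.** The SE of the standardised difference in rate is √(1/33 + 1/17) = 0.299. P(rate favours IFB-088 by more than 0.3 SD) = P(Z > 1.005) = 15.7%, with the same again favouring placebo. In those trials the mean imbalance is 0.299 × φ(1.005)/0.157 = 0.456 SD.

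The planned model removes the share of this that baseline carries, which leaves 5 × r × 0.456 × (1 - ρ²), where 1 - ρ² = 0.564 / 0.360 / 0.190:

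- r = 0.2: 0.26 / 0.16 / 0.09 points
- r = 0.5: 0.64 / 0.41 / 0.22 points

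Simulation gives 0.23-0.67 / 0.15-0.41 / 0.08-0.20 over r = 0.2 to 0.5, the same within simulation error. After adding rate, the shift is about zero.

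For the largest case, the SE of the planned estimate is 5 × 0.299 × √0.891 = 1.41, and 0.67/1.41 = 0.48.

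**Limits.** These shifts scale with the assumed SD. Deaths scored 0 and the imputation of drop-outs are not modelled here.

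**The case against.** **It is a preference, since the planned model is valid.** This stands. A reader might infer that omitting rate biases the result or inflates type I error. It does neither: trials favouring IFB-088 and trials favouring placebo balance out, and the shift in Step 4 exists only after conditioning on an observed imbalance.

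**The protocol chose this covariate.** This also stands. A reader might infer that the SAP dropped a promised adjustment, because Protocol 8.1.5.2 mentions a model "analysed with an ANCOVA with pre specified fixed factors and covariates". That wording concerns the pattern-mixture sensitivity analysis and names no covariate. The same section gives baseline ALSFRS-R as the only continuous covariate of the main MMRM. The documents left room for further adjustment but did not promise it.

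**The gain may be nil, and the best figures need very early onset.** This stands. Eligible patients need probable or definite ALS and at least a month of stable riluzole, and Protocol 1.1.1 describes diagnosis as often slow. A 3-month floor is therefore the optimistic end. At 6 and 9 months the best variance gains are 8% and 4%.

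**The subgroup models already include rate and time from onset.** Partly right. Each enters as a median split alongside baseline score, so some information on imbalance will be available. But the outputs are effects within halves and an interaction p-value, not one overall adjusted effect.

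**More than one line of the SAP is affected.** Correct. Estimand #1 imputes patients with no Month 3 score from baseline score alone, and estimand #3's imputation model holds only treatment and ALSFRS-R scores. The fix has to cover this.

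**Conclusion.** The point holds as an optional improvement, not an error. The plan collects a plausible prognostic variable, displays it by arm and uses it for subgroups, yet never uses it to adjust the overall Month 6 effect. Under the stated assumptions the effect on variance runs from a 2% loss to a gain of 14%, 8% or 4% at onset floors of 3, 6 or 9 months. The main benefit is a pre-specified answer if the arms differ by chance in prior decline. The size rests wholly on assumed inputs: the SD, the spread of onset times and the correlation of rate with on-study decline.

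Two stronger readings are not supported. One is that the primary model must change: a possibly nil gain on an unpowered secondary endpoint does not require that. The other is that baseline neurofilament light chain should be added as well: no gain from it can be shown from the documents, and SAP 5.11.5.2.1 leaves its missing values unimputed.

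**What to change.** Before unblinding, pre-specify an ANCOVA for estimand #1 on the FAS with treatment, baseline ALSFRS-R and continuous progression rate (symptom onset to screening, as already calculated). Report one overall treatment effect with its confidence interval beside the planned model. A named sensitivity analysis is enough; making it primary is the sponsor's choice.

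Within that analysis, include rate in the regression that imputes patients with no Month 3 score (SAP 2.3, Table 1). If the adjustment is extended to estimand #3, include rate in its imputation model too (SAP 5.11.2.2, sensitivity analysis #2). Imputation and analysis then agree. Record the addition in SAP section 7.

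The cost is one of 47 residual degrees of freedom, about 2.2% more variance if rate predicts nothing, and a little programming. No new data are needed.

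The SAP is dated 12 November 2024 and the protocol planned last patient out for the third quarter of 2024, so the documents do not show whether the blind still holds. If it is already broken, report the analysis under the post-lock addendum described in SAP section 5, labelled as such.

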5.11.2.2 Sensitivity analyses

Sensitivity analysis #1 considering estimand #2:

The same analysis proposed for the primary analysis will be provided for estimand #2

Sensitivity analysis #2 considering estimand #3:

The same analysis proposed for the primary analysis will be provided for estimand #3.

Missing data due to death whatever the cause: the ALSFRS-R score at month 6 will be imputed by the worst value (i.e. 0).

For the MAR multiple imputation part, the model used for imputation will be done without patients who died before V4.

First step (if necessary):

If the missing pattern is not monotone (missing values at month 3 and not at month 6), a first step will use the Markov Chain Monte Carlo (MCMC) method to impute data only partially to obtain a dataset with monotone missingness as proposed by O'Kelly, Michael; Ratitch, Bohdana. Clinical Trials with Missing Data: A Guide for Practitioners (Statistics in Practice), Wiley.

This first step assumes data are missing at random to impute intermittent (non- monotone) missing data using MCMC method with single chain, non-informative prior, 200 burn-in iterations, 50 iterations between imputations in a chain and Expectation-Maximization algorithm (using mcmc chain=single impute=monotone prior = jeffreys options) and seed of xxxxx.

The imputation model will be fitted **by treatment** and will include the following terms in this specific order:

- ALSFRS total scores in order: at baseline, Month 3 and Month 6

Note: imputed values will be rounded to the nearest integer.

Second step:

STATISTICAL ANALYSIS PLAN		
InFlectis BioScience	Sponsor:	InFlectis BioScience
	Protocol Number:	P288ALS
VERSION 1.0 NOV 12, 2024		

If step 1 is necessary, the output data set from Imputation Model Step 1 will be the input for Step 2 using Monotone Regression. The second imputation model will generate one imputation for each of previous multiply imputed datasets of MI1 (i.e. by _Imputation_) and a seed of yyyy. The model will include only the following variables:

- Randomized Treatment (as a classification variable)
- ALSFRS total scores in order: at baseline, Month 3 and Month 6

If step 1 is not necessary, the imputation model will use monotone regression and generate 50 imputations and a seed of 293654. The model will include only the following variables:

- Randomized Treatment (as a classification variable)
- ALSFRS total scores in order: at baseline, Month 3 and Month 6

Note: imputed values will be rounded to the nearest integer. Imputed value higher than 48 will be replaced by 48 and imputed value lower than 0 will be replaced by 0.

Third step:

50 estimates of treatment LS means and LS means differences with standard errors from ANCOVA model of the multiply imputed datasets will be pooled using PROC MIANALYZE to produce an overall estimate (the mean of the 50 estimates) and a standard error (based on Rubin's formula) with associated 95% confidence interval and p-value. Pooled adjusted LS means of change from baseline ALSFRS-R score with standard error and 95% confidence interval will be presented for each treatment group and the pooled estimated LS mean difference between Active and Placebo will be presented with standard error and 2-sided p-value.

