3 SAMPLE SIZE

The minimum required sample size for this study has been estimated at 42 evaluable patients. Since it is an exploratory safety study, it has not been based on a formal sample size calculation. However, with regard to the primary safety endpoint, it is worth noting that 28 patients enrolled in the IFB-088 arm will be sufficient to observe at least one SAE which incidence is greater than or equal to 5% (10% resp.) with a probability of at least 76.2% (94.8% respectively). In addition, 42 patients are also considered sufficient to observe some numerical efficacy signal on some key parameters. Assuming a 15% drop-out rate, 50 patients were to be randomised.

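### The SAP gives no degrees of freedom for the pooled Estimand #3 result; with large-sample Rubin df its 95% CI would be about 3–4% narrower than with small-sample df

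*SAP*

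**What the plan says.** SAP 2.3, Table 1, makes Estimand #1 (single imputation) primary for month-6 ALSFRS-R change and Estimands #2 and #3 sensitivity analyses. Under Estimand #3 every death is set to 0, and scores missing through drop-out are multiply imputed under missing at random.

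SAP 5.11.2.2 (Sensitivity analyses) carries the model over: "The same analysis proposed for the primary analysis will be provided for estimand #3". That model, in 5.11.2.2.1, is an "analysis of covariance (ANCOVA) model including treatment (IFB-088 vs placebo), and baseline ALSFRS-R score as continuous covariates". It has three mean parameters: intercept, treatment and baseline.

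The third step then takes "50 estimates of treatment LS means and LS means differences with standard errors from ANCOVA model of the multiply imputed datasets". These "will be pooled using PROC MIANALYZE to produce an overall estimate (the mean of the 50 estimates) and a standard error", the latter "based on Rubin's formula) with associated 95% confidence interval and p-value". The text stops there. It gives no complete-data df, names no small-sample adjustment, and does not say that large-sample df will be used.

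**The concern.** Rubin's large-sample df depend only on the number of imputations and the fraction of missing information. They take no account of how many patients were analysed. In a trial of about 50 patients with 50 imputations they amount to a near-normal reference distribution. Incomplete data would then be credited with more df than the same data would have if complete.

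Two things make this worth settling. First, Estimand #3 exists to be read beside Estimand #1, whose ANCOVA uses a t reference with N minus 3 df. The two should differ in their missing-data assumptions, not also in their reference distribution. Second, the protocol (8.1.5.2) had specified Kenward-Roger df for its mixed model. SAP section 7 replaces that model with ANCOVA and does not say what takes over the small-sample role where imputations are pooled.

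**Working it through.** **The plan's own figures.** The SAP states no df figure, so there is none to reproduce. The sample-size figures in SAP section 3 do reproduce:

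- At least one SAE among 28 active patients: 1 − 0.95^28 = 0.762 and 1 − 0.90^28 = 0.948, as stated.
- Number randomised: "The minimum required sample size for this study has been estimated at 42 evaluable patients", and 42/0.85 = 49.4, rounded up to 50, which agrees with "Assuming a 15% drop-out rate, 50 patients were to be randomised".

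**Inputs.**

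- m = 50 imputations (SAP 5.11.2.2).
- Three ANCOVA mean parameters (SAP 5.11.2.2.1).
- N = 50 planned, or 42 as the stated minimum (SAP section 3).
- λ, the fraction of missing information, is not in the documents and is assumed, with range 0.02–0.30. The 15% drop-out rate is only a guide to it: month-3 scores recover some information, and deaths set to 0 add no between-imputation variance.

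**Formulas.**

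- λ = (1 + 1/m)B/T, with B the between-imputation and T the total variance.
- Large-sample Rubin df: ν_m = (m − 1)/λ².
- Complete-data df: ν_0 = N − 3.
- Barnard-Rubin df: 1/ν = 1/ν_m + 1/ν_obs, with ν_obs = (1 − λ)ν_0(ν_0 + 1)/(ν_0 + 3).

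**Lower bound.** Since λ cannot exceed 1, ν_m is at least 49. With N = 50, ν_0 = 47, so the large-sample df exceed the complete-data df whatever the missingness.

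**Worked case, N = 50, λ = 0.15.**

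- ν_m = 49/0.0225 = 2,178.
- ν_obs = 0.85 × 47 × 48/50 = 38.4.
- ν = 1/(1/2,178 + 1/38.35) = 37.7.
- 95% critical values are 1.961 (large-sample) and 2.025 (adjusted). The ratio is 1.033, so the large-sample interval is 1 − 1/1.033 = 3.2% narrower.

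| N | λ | Large-sample df | Adjusted df | 95% critical values | CI narrower by | p = 0.050 becomes | p = 0.200 becomes |
|---|---|---|---|---|---|---|---|
| 50 | 0.02 | 122,500 | 44.2 | 1.960 / 2.015 | 2.7% | 0.0563 | 0.2067 |
| 50 | 0.05 | 19,600 | 42.8 | 1.960 / 2.017 | 2.8% | 0.0565 | 0.2069 |
| 50 | 0.15 | 2,178 | 37.7 | 1.961 / 2.025 | 3.2% | 0.0573 | 0.2077 |
| 50 | 0.30 | 544 | 29.9 | 1.964 / 2.043 | 3.8% | 0.0589 | 0.2093 |
| 42 | 0.15 | 2,178 | 31.1 | 1.961 / 2.039 | 3.8% | 0.0589 | 0.2093 |
| 42 | 0.30 | 544 | 24.8 | 1.964 / 2.060 | 4.7% | 0.0608 | 0.2113 |

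**Coverage.** Null trials were simulated with assumed SDs and missingness.

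- 25,000 trials per scenario: 95% intervals covered 94.4–94.7% with large-sample df and 95.0–95.5% with the adjustment (Monte Carlo SE about 0.14 points). The 80% intervals covered 78.7–79.6% and 79.4–80.3% (SE about 0.25 points).
- 4,000 trials per scenario (33 v 17 patients, 15% missing at month 6): large-sample coverage was 94.9% without deaths and 95.6% with 6% deaths set to 0, against 95.6% and 96.1% adjusted. With an SE of about 0.3 points, this run is too small to show a shortfall of the size seen in the larger one.

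**The case against.** The strongest reply is that nothing wrong has been specified. The SAP is silent on df; it does not choose the large-sample version. A reader might infer that the procedure falls back to large-sample df when none are supplied, but the documents do not say so, and a programmer could supply them unprompted. This stands: the point is a gap with a conditional consequence, not a demonstrated wrong choice.

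A reader might also take 47 as the trial's complete-data df. No document gives that figure. It requires all 50 planned patients to be in the FAS with a baseline ALSFRS-R value, and no actual count is given. This stands too, and it rules out writing 47 into the plan.

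Third, the effect is slight. Efficacy is secondary, unpowered and tested at a nominal two-sided 0.20, and no decision rule hangs on Estimand #3. Its handling of deaths and drop-outs can move the estimate and standard error relative to Estimand #1, whereas the df choice changes neither. All this is correct and limits the weight of the point. It is not a reason to leave the reference distribution open when closing it is free. The smaller simulation's near-nominal coverage is not a reason either, given its Monte Carlo error.

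**Conclusion.** The SAP should state the df for the pooled ANCOVA. If large-sample Rubin df are used, they exceed the complete-data error df for any missingness at the planned size. The Estimand #3 95% CI is then about 3–4% narrower than it should be, a p of 0.050 should be about 0.056–0.059, and a p of 0.200 about 0.208. The direction is certain under that condition. The size rests on the assumed missing information (0.02–0.30) and on 50 patients analysed; with 42 it is slightly larger (3.8% at 15% missing information). The simulated loss of coverage is about half a percentage point or a little more at the 95% level.

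A reader might infer that the trial's efficacy conclusion is at risk. The documents do not support that: Estimand #1 is singly imputed and involves no pooling, so the primary ALSFRS-R result is untouched, and only one sensitivity analysis of a secondary endpoint is affected. This is a free improvement, not a flaw in the design.

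**What to change.** Add to the third step of SAP 5.11.2.2 that the complete-data error df of the ANCOVA are supplied to PROC MIANALYZE through the EDF option, so that Barnard-Rubin small-sample df are used for the pooled CI and p-value. Define them as the number of patients analysed minus the number of model parameters, which is N − 3 for the present model. Here N counts every FAS patient with a baseline ALSFRS-R value, including those with imputed scores. Do not fix the value at 47.

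The cost is one sentence and one program option; no data, visits or sample size change. SAP section 5 allows amendment before the blind is broken; after final database lock it would go into the SAP addendum described there.
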